### ***Replication***

Replication methods provide a relatively simple way of estimating variances and have some advantages over other variance estimation methods (e.g., linearization approach). The basic idea behind the replication approach is to repeatedly select portions of the sample (“replicates”), to calculate the estimate of interest for each replicate, and then use the variability among these

estimates to estimate the variance of the full sample statistics. Different approaches can be used to creating these replicates.

For WIC ITFPS-2, 40 replicates will be created, and the replication approach that will be used is a modified balanced repeated replication (BRR) method suggested by Fay (Judkins 1990). When estimating the variance of ratios of rare subsets, one problem that occasionally arises from standard BRR is that one or more replicate estimates will be undefined due to zero denominators. Instead of increasing the weights of one half-sample by 100 percent and decreasing the weights of the other half-sample to zero as in standard BRR, Fay's method perturbs the weights by  $\pm 100(1-K)$  percent where K is referred to as "Fay's factor." The perturbation factor for standard BRR is 100 percent, or  $K=0$ . For WIC ITFPS-2,  $K=0.5$  will be used.

In order to create the replicates (and also to define the variables needed for Taylor series linearization variance estimates), it is necessary to define variance strata and variance units. Each stratum defined for the selection of first-stage sampling units will constitute a separate variance stratum. The two first-stage units selected each stratum will comprise the first and second variance units. For each set of weights defined in Table 6-1, we will develop a set of "replicate" weights in addition to the full-sample weights. In order to appropriately reflect the effects of the various stages of weighting on the variances of survey estimates (Ernst and Williams, 1987), the procedures used to compute the full-sample weights (described in Section 6.2) will be repeated for each of the replicates.

This procedure will slightly overestimate variances since it will not account for the first-stage finite population correction (fpc) factor. The first stage fpc factor is the reduction in variance due to the fact that the first-stage sampling units will have been selected without replacement rather than with replacement. A more complex version of Fay's method has been developed that captures this fpc (see for example Rizzo and Judkins, 2004, which all includes references to earlier related work). However, these have not been routinized at Westat and do not appear to be worth the extra difficulty in implementation for WIC ITFPS-2 given that most service sites are small and will have very small chances of selection, rendering the fpc negligible.

---

Judkins, D. Fay's method for variance estimation. *Journal of Official Statistics*, 1990; 6: 223-240.

Rao, J.N.K., and Shao, J. Modified balanced repeated replication for complex survey data. *Biometrika*, 1999;; 86:403-415.

### ***Taylor Series Linearization***

Taylor series linearization uses a mathematical approximation to approximate a nonlinear statistic with a linear form. The variance of the nonlinear statistic is approximated by the variance of the linear function. Software packages that use Taylor series linearization to estimate variances of statistics from complex sample surveys require the user to specify design information including “stratum” and “cluster” variables. Unlike those based on replication methods, variance estimates based on Taylor series linearization do not fully capture the effects of all of the weight adjustments; however, in most cases, the differences between Taylor series standard errors and replication-based standard errors are not large. The “stratum” and “cluster” variables that allow users to compute variance estimates using Taylor series linearization will be provided on the WIC ITFPS-2 files.

This page left intentionally blank

We will conduct analyses to answer the 60 research questions articulated in the RFQ as well as supplementary questions. Additionally, we will repeat most of the past analyses from the FNS-sponsored WIC-IFPS-1 and the two Gerber/Nestle Feeding Infants and Toddlers Studies (FITS). We will compare current findings to relevant past work and to current objectives and standards.

## 7.1 Repeating the Analyses of Past Studies

The most relevant past research is the WIC-IFPS-1 as it focused specifically on the WIC population while the other major studies of feeding practices were general population studies. Therefore, in repeating past analyses the focus is primarily on the WIC-IFPS-1. We then reviewed the Gerber/Nestle FITS studies I and II, the FDA-sponsored IFPS, and the WIC Birth Month Study from the perspective of the additional research questions and analyses they contribute beyond those addressed by the WIC-ITFPS-1. The FITS are substantially different from the WIC-IFPS-1 and focus primarily on nutrient intake, which complements the work done in the WIC-ITFPS-1 and provides more detail on nutrient intake. Additionally, although it uses cross-sectional data, the FITS include analyses of both infant and toddler feeding practices through 24 months. In contrast, the FDA-sponsored IFPS address basically the same research questions as the WIC-IFPS-1 but cover the general population. Additionally, these studies collected detailed information on topics that are only tangentially relevant to WIC objectives such as food safety practices, infant and mother sleep patterns, and infant food related-health problems. To include these topics in the data collection would increase the response burden beyond acceptable levels. Given the overlap in research question and the tangential nature of some of their additional research, we will not separately replicate the analyses from the FDA IFPS. Similarly, the WIC Birth Month Study also heavily overlaps with many of the topics addressed in WIC IFPS-1 but addresses them in more detail as the study only covers nutritional issues during the first month of life. We repeat analyses from the Birth Month Study to the extent that our data collection supports. Finally, because the schedule of interviews includes both infant and toddler data collection, some of the WIC-IFPS-1 analyses will be repeated using different time points. Table 7-1 provides a summary of the analyses we intend to repeat and those we do not intend to repeat. Additionally, in Appendix A, we provide a listing of all

the tables and figures in the final WIC-IFPS-1 report noting whether we will repeat this work or no. In the cases in which we will not be repeating the work we provide an explanation for this decision.

**Table 7-1. Summary of analyses to be repeated from previous studies**

Primary topics	Summary analyses repeated	Analyses not repeated
WIC-IFPS-1		

 
■ Breastfeeding patterns, intensity, and duration
 
■ Reasons for stopping breastfeeding
 
■ Transitional and complementary feeding
 
■ Timing of these decisions
 
■ Supplemental foods
 
	
 
■ Tabulations and comparisons (Chi2 tests) by subgroups (e.g., percentage initiating breastfeeding by socio-demographics)
 
■ Frequencies over time (e.g., percentage still breastfeeding by age of infant)
 
■ Factor analysis (e.g., dimensions for breastfeeding attitudes and knowledge)but items will be updated
 
■ Logistic regressions for probability of an event (e.g., initiating breastfeeding)
 
■ Survival analyses for time until an event (e.g., time until cereals are introduced)
 
	
 
■ Interim models that only use a subset of the covariates
 
■ OLS regressions of breastfeeding frequency (e.g., counts of number of breastfeed at month1)
 

FITS I and II		
Nutrient intake	
 
■ Food and nutrient intake estimates
 
■ Frequencies over time(e.g., percentage consuming vegetables by age of infant)
 
■ One-day nutrient intake distributions (e.g., overall intake and prevalence of inadequate and excess)
 
	
 
■ Tabulations of developmental milestones
 

FDA		
As the FDA study significantly overlaps with the WIC-IFPS-1 and FITS, no additional analyses will be repeated from the FDA study		

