**Table 4-1. Interview events for core and supplemental sample**

WIC enrollment	INTERVIEW											
	Infant										Toddler	
	Enrollment	Prenatal	1 month	3 months	5 months	7 months	9 months	11 months	13 months	15 months	18 months	24 months
Core Sample – Prenatal	✓	✓	✓	✓	✓	✓	✓	✓	✓	✓	✓	✓
Core Sample – Infant <6 wks	✓		✓	✓	✓	✓	✓	✓	✓	✓	✓	✓
Core Sample – infant 6 wks-2.5 mos				✓	✓	✓	✓	✓	✓	✓	✓	✓
Supplemental Sample – Prenatal	✓		✓			✓			✓			✓
Supplemental Sample – Infant <6 wks	✓		✓			✓			✓			✓
Supplement Sample – Infant 6 wks-2.5 mos				✓		✓			✓			✓

We will conduct the telephone interviews in English and Spanish and participants will be paid a \$20 incentive on completion of each interview. All post-birth interviews will include a 24-hour dietary recall using the AMPM. Participants will receive a package of measuring guides to help them report

their child's portion sizes during the interview. We will collect replicate intakes on a 10 percent subsample of toddlers at 13, 15, 18, and 24 months in order to estimate "usual" intake.

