## 7.2 Key Analytical Variables

### ***Outcomes and Key Feeding Decisions***

To answer the research questions and update past analyses, we will assess feeding practice decisions, child nutrient and food intake, and weight outcomes. As the variety of foods infants consume is very limited in the initial months of a child’s life, the feeding practices the caregiver employ are key to nutrient intake. In contrast, once the child is eating a variety of foods, direct food intake measures become the most important measures of dietary quality. The main feeding practice decisions and outcomes are listed below. All variables will be examined by frequencies and how they vary by key

socio-demographics, however, only those that are not italicized will be used as outcomes in the causal model estimations.

- **Breastfeeding Decisions.** *Intent to breastfeed*, initiation of breastfeeding, *first hospital feeding*, breastfeeding at hospital discharge
- **For Those Who Breastfeed.** *Use of breast pump*, time until formula supplementation, time until breastfeeding cessation
- **Other Infant Feeding Practices.** *Number of feedings per day*, time until cereal, time until baby foods (by type), *duration of bottle use*, *timing of feeding transition*
- **Nutrient Intake and Weight Outcomes.** *Foods eaten by type*, *calorie intake per kilogram of body weight*, *usual nutrient intakes relative to Estimated Requirements (EARs) (where these exist and Adequate Intakes (AIs) otherwise)*, *nutrient densities*, *nutrient intakes relative to UL (where these exist)*, *weight-for-length*, *weight/length gain (0-6 months)*, *weight/length gain (6-12 months)*.

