To translate the dietary data obtained from our interviews into measures of usual nutrient intake, we will use the NCI method developed by researchers at the NCI, the USDA, and elsewhere. The NCI method is a unified framework for estimation of usual intake of nutrients and foods. It models usual intake as the product of the probability of consumption on a given day and the average amount consumed, which is conditional on having consumed a positive amount. It takes into account zero-consumption days and reported consumption-day amounts that are positively skewed, and distinguishes between within-person and between-person variation in consumption. It also allows for efficient estimation of usual intake for subgroups. Instead of stratifying the sample by subpopulation and estimating usual intake separately for each subgroup, covariates defining subgroups are included in the NCI model, such that (difficult to estimate) variance components may be estimated simultaneously for the full sample, and only covariate values differ. For subgroups of respondents comprising a relatively small proportion of the full sample, the efficiency gains from this capability are likely to be relatively substantial.

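### Table 7-1 ties prevalence of inadequate and excess nutrient intake to one-day distributions, and Section 7.2 omits *usual* for the UL outcome; both conflict with the usual-intake plan elsewhere, and nothing says which governs.

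*Combined protocol and SAP*

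**What the plan says.** Section 7.1 introduces Table 7-1 as the summary of past analyses that the study will and will not repeat. In the FITS block, the column of repeated analyses includes "One-day nutrient intake distributions (e.g., overall intake and prevalence of inadequate and excess".

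Section 7.2 (Outcomes and Key Feeding Decisions) lists the nutrient outcomes. Against requirements, the outcome is "usual nutrient intakes relative to Estimated Requirements (EARs) (where these exist and Adequate Intakes (AIs) otherwise". Against the upper level, it is "nutrient intakes relative to UL (where these exist", without the word *usual*. The section then says: "To translate the dietary data obtained from our interviews into measures of usual nutrient intake, we will use the NCI method". It describes that method as one that "distinguishes between within-person and between-person variation in consumption".

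Section 4.8 supplies the data for this: "We will collect replicate intakes on a 10 percent subsample of toddlers at 13, 15, 18, and 24 months". A footnote there takes the corresponding adjustment for infants from NHANES.

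The nutritional-intake block of Table 7-2 lists usual-intake distributions for infants and toddlers, covering micronutrients, macronutrients, energy and fiber. Table B-1 answers research question 16 with the same kind of table.

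**The concern.** EAR and UL cut-offs apply to habitual intake. A single 24-hour recall carries the child's day-to-day variation as well as the differences between children, so its distribution is wider than that of usual intake. Counting children beyond a cut-off in that wider distribution misstates the share whose habitual intake lies beyond it. The plan adopts the NCI method to deal with this, yet the Table 7-1 entry attaches the prevalence figures to the unadjusted distribution.

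Assessing over- and underfeeding is one of the seven primary objectives in Section 1.1, and these proportions bear directly on it. An analyst working from Table 7-1 and from the UL item in Section 7.2 could compute the share above the UL from single recalls and be within the text. Another analyst, working from the NCI paragraph, would report a different number for the same quantity.

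**Working it through.** **No plan figure to reproduce.** The documents state no prevalence, cut-off value or variance ratio for this analysis. The check therefore has two parts: a comparison of the texts, and an illustration of size under stated assumptions.

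**1. The texts compared.**

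| Place | Basis for the intake measure |
|---|---|
| Table 7-1, FITS block | One-day distribution, with prevalence of inadequacy and excess as the example |
| Section 7.2, EAR/AI outcome | Usual intake |
| Section 7.2, UL outcome | Not stated |
| Section 7.2, method paragraph | Usual intake by the NCI method |
| Section 4.8 and its NHANES footnote | Data to adjust to usual intake: replicates in toddlers, NHANES in infants |
| Table 7-2, nutritional intake; Table B-1, question 16 | Usual-intake distributions |

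For inadequacy, Table 7-1 contradicts an explicit usual-intake definition. For excess, the outcome definition is silent and Table 7-1 is the only text that names a basis for prevalence. No sentence says that Table 7-1 is superseded or serves only for comparison with FITS.

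**2. Size if one-day data were used.** Assumptions:

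- Usual intake is normal with between-person SD *s*.
- A one-day intake equals usual intake plus independent normal error with no bias in the mean.
- The within- to between-person variance ratio *r* is 0.5, 1 or 2. These values are assumed, since the documents give none.

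If a share *p* of children lies beyond the cut-off on usual intake, the cut-off sits at z(p) = Φ⁻¹(p) in units of *s*. The one-day SD is s·√(1 + r), so the one-day share is

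p₁ = Φ( z(p) / √(1 + r) ).

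By symmetry this serves for a share below the EAR or above the UL.

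For p = 5%, z = −1.645:

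- r = 0.5: −1.645 / 1.225 = −1.343, so p₁ = 9.0%
- r = 1: −1.645 / 1.414 = −1.163, so p₁ = 12.2%
- r = 2: −1.645 / 1.732 = −0.950, so p₁ = 17.1%

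The same formula at other values:

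| True share on usual intake | r = 0.5 | r = 1 | r = 2 |
|---|---|---|---|
| 2% | 4.7% | 7.3% | 11.8% |
| 5% | 9.0% | 12.2% | 17.1% |
| 10% | 14.8% | 18.2% | 23.0% |
| 50% | 50.0% | 50.0% | 50.0% |
| 75% | 70.9% | 68.3% | 65.2% |

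The error is upward below 50%, zero at 50%, and downward above it.

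**The case against.** The strongest reply is that the operative plan already rests on usual intake. Table 7-1 is a summary of earlier work to be repeated. Section 7.5 describes Table 7-2 as the list of all tables and figures, and none of its titles is a one-day intake distribution; the FITS distribution tables appear there as usual-intake tables. The EAR/AI outcome says *usual*, and Section 7.2 adds that all variables will be examined by frequencies, which for that outcome means a frequency of usual intake. On this view the missing adjective before the UL item is a slip in a list whose previous entries carry it. A one-day figure might also be wanted, because comparison with FITS is a stated objective.

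Most of this stands, and it rules out several stronger readings that a reader might draw:

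- That one-day data are the plan, or the only stated basis for inadequacy. Section 7.2 says otherwise for the EAR/AI outcome.
- That the NCI model and replicate recalls would bring no benefit for the prevalence figures. That would follow only if Table 7-1 overrode Section 7.2, and nothing says it does.
- That the plan will call a share below an AI a prevalence of inadequacy. It says only that intakes are set against EARs "where these exist and Adequate Intakes (AIs) otherwise", which is compatible with comparing means or medians.
- That tables of proportions beyond the EAR or UL are absent. Table 7-2 gives titles and points to source pages that are not in the documents, so what those tables contain cannot be settled.

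The reply does not remove the contradiction. Table 7-1 states what will be repeated and names prevalence as its example, the UL item is silent, and no rule of precedence is given. The wish for a like-for-like FITS comparison is a reason to label a one-day figure, which the plan does not do.

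**Conclusion.** The point holds as an unresolved inconsistency with a material consequence if the wrong text is followed. It is clearest for the UL, where the outcome definition does not call for usual intake and Table 7-1 points to one-day data. For inadequacy, Section 7.2 is explicit and Table 7-1 contradicts it.

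The size is conditional. With normal intake and assumed variance ratios of 0.5 to 2, a true 5% beyond a cut-off would be reported as 9.0% to 17.1%, about 1.8 to 3.4 times the true value. Section 7.2 notes that consumption amounts are positively skewed, so the actual figures would differ and the point of no bias would not sit exactly at 50%. It would be wrong to say that one-day data inflate prevalence in general: under the same assumptions a true 75% would appear as 70.9% to 65.2%.

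**What to change.** Three changes of wording:

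1. In Table 7-1, restrict the one-day entry to mean intakes, percent consuming, or a like-for-like comparison with FITS that is labelled as one-day and not interpreted as prevalence of inadequate or excess usual intake.
2. In Section 7.2, insert *usual* before the UL item, so that the EAR/AI and UL outcomes have the same basis.
3. In Table 7-2, state that proportions below the EAR and above the UL come from the NCI usual-intake distribution.

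The cost is small. The NCI model and the data for it are already planned, so the proportions come from the same fit and no new data collection is needed. The one drawback is that any one-day comparison with FITS needs a separate, clearly labelled figure beside the usual-intake result.

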## 7.2 Key Analytical Variables

### ***Outcomes and Key Feeding Decisions***

To answer the research questions and update past analyses, we will assess feeding practice decisions, child nutrient and food intake, and weight outcomes. As the variety of foods infants consume is very limited in the initial months of a child’s life, the feeding practices the caregiver employ are key to nutrient intake. In contrast, once the child is eating a variety of foods, direct food intake measures become the most important measures of dietary quality. The main feeding practice decisions and outcomes are listed below. All variables will be examined by frequencies and how they vary by key

socio-demographics, however, only those that are not italicized will be used as outcomes in the causal model estimations.

- **Breastfeeding Decisions.** *Intent to breastfeed*, initiation of breastfeeding, *first hospital feeding*, breastfeeding at hospital discharge
- **For Those Who Breastfeed.** *Use of breast pump*, time until formula supplementation, time until breastfeeding cessation
- **Other Infant Feeding Practices.** *Number of feedings per day*, time until cereal, time until baby foods (by type), *duration of bottle use*, *timing of feeding transition*
- **Nutrient Intake and Weight Outcomes.** *Foods eaten by type*, *calorie intake per kilogram of body weight*, *usual nutrient intakes relative to Estimated Requirements (EARs) (where these exist and Adequate Intakes (AIs) otherwise)*, *nutrient densities*, *nutrient intakes relative to UL (where these exist)*, *weight-for-length*, *weight/length gain (0-6 months)*, *weight/length gain (6-12 months)*.

To translate the dietary data obtained from our interviews into measures of usual nutrient intake, we will use the NCI method developed by researchers at the NCI, the USDA, and elsewhere. The NCI method is a unified framework for estimation of usual intake of nutrients and foods. It models usual intake as the product of the probability of consumption on a given day and the average amount consumed, which is conditional on having consumed a positive amount. It takes into account zero-consumption days and reported consumption-day amounts that are positively skewed, and distinguishes between within-person and between-person variation in consumption. It also allows for efficient estimation of usual intake for subgroups. Instead of stratifying the sample by subpopulation and estimating usual intake separately for each subgroup, covariates defining subgroups are included in the NCI model, such that (difficult to estimate) variance components may be estimated simultaneously for the full sample, and only covariate values differ. For subgroups of respondents comprising a relatively small proportion of the full sample, the efficiency gains from this capability are likely to be relatively substantial.

### **Comparison Groups and Covariates**

We will assess participants' outcomes and decisions by subgroups to identify subpopulation differences. Using the conceptual causality models and the past research as a guide, we will model these outcomes and decisions as a function of a set of covariates that are possibly predictive of the outcome (or decision) under study. The core analytical comparison groups will be similar to the

---

<http://riskfactor.cancer.gov/diet/usualintakes/details.html>

socio-demographic categories that were used in the past studies and will include race, ethnicity, mother's age, mother's education, mother born in the United States, father living in the home, poverty level, and infant's birth order. Our comprehensive data collection will allow us to explore the impact of a few additional socio-demographic variables such as household food security and acculturation on feeding practices and nutrition outcomes.

As we showed in the conceptual models, in addition to these socio-demographic variables, data on maternal and family health, the mother's attitudes, beliefs and knowledge, the mother's experience and receipt of advice, the mother's hospital experience, the mother's lifestyle choices, and toddler feeding practices, will serve as categories of covariates in the analyses. We expect that a large number of the potential individual variables within these covariate groups will be correlated as on many topics we are asking specific information about attitudes and behaviors. Therefore, many of the interview questions will be highly related. For example, to obtain information about the mother's attitudes, beliefs and knowledge regarding breastfeeding will require asking a battery of questions, with each question revealing a specific viewpoint. It is likely that women who are pro-breastfeeding answer the set of questions one way while those who are not answer differently which would result in highly correlated responses among participants. Including highly correlated variables in a regression model can make interpreting results difficult and lead to multicollinearity. We will explore using principal component analysis to transform sets of potentially correlated variables into a set of uncorrelated composite measures. We will explore using this data reduction technique to summarize the responses to questions regarding: (1) maternal attitudes, belief, and knowledge about breastfeeding, (2) hospital experience and (3) toddler feeding practices. Because the development of meaningful composite measures is dependent on the correlation between items, we are not able to guarantee, in advance, that this technique will yield useful composites in all cases.

